necessary. We intend for the BREATHE cohort to be a source of potential subjects for future studies. For studies which involve a clinical trial of an investigational product or diagnostic method we will adopt a 'Trials within cohorts' design (TwiC)^{11,12}. The method identifies participants for a trial from an existing cohort who are suitable for an upcoming interventional study. Participants are randomised to an intervention arm and further consent is obtained. Those not randomised to the intervention arm will continue standard care in line with the BREATHE study and act as the control group but without additional consent^{11,12}. We will describe the two stage consent TwiC process at the point of consent into the BREATHE cohort with a choice to opt out if the participant wishes. Participants can still consent to participate in the BREATHE study without consenting to be contacted about future studies.

BREATHE-ILO sub-study

Outcomes (Report of outcomes at 2 years):

- 1. Understanding the incidence of CLE/P confirmed ILO in patients referred to the Complex Airways Service.
- 2. Understanding the incidence of BPD in patients referred for CLE/P.
- 3. An analysis of the predictors of ILO or BPD in patients referred to the Complex Airways Service.
- 4. An analysis of the predictors of response to interventions for ILO and BPD.
- 5. An analysis of whether the diagnosis and treatment of ILO and BPD improve quality of life for the patient and reduce treatment burden.

Inclusion Criteria

- 1. Participant is willing and able to give informed consent for participation in the study
- 2. Known or suspected asthma mimics or inducible laryngeal obstruction

Exclusion Criteria

- 1. Participants who lack capacity to consent for themselves.
- 2. Aged below 16 years

Recruitment

Recruitment for the BREATHE-ILO sub study will be identical to the recruitment processes of the BREATHE platform study (see section below). If a clinician suspects an underlying diagnosis of ILO or asthma mimics based on their history or from previously recorded investigations then they will be asked to consider consent to the BREATHE-ILO sub study. Participants can be enrolled onto both studies simultaneously.

PARTICIPANT IDENTIFICATION

Study Participants

Any patient over 16 years seen in the Complex Airways Clinic at the North Bristol NHS Trust

Inclusion Criteria

1. Participant is willing and able to give informed consent for participation in the study

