Subsequent visits and investigations will be determined as per routine clinical care. Baseline data will be taken at the initial clinic appointment, at 6 (+/- 4months), 12(+/- 4months) and 24(+/- 4months) months after recruitment. These timepoints do not represent patient visits as they will be dictated by the clinician in charge of the participants airways care in line with standard care. They are the timepoints at which the participants medical records are scrutinised and data pertaining to their Airways disease entered into REDcap. Patient's may also be discharged and re-referred by primary care and participants will continue in the study in a new or different pathway. Each pathway will record data for a maximum of 24 months (see study flow chart). If a participant is under the care of the

Date and version No: 16/08/2023. V1.1

Complex Airways Team for longer than the 2 year data collection schedule then we will store the outcome from annual MDT decisions until they are discharged from the service or the study ends.

Discontinuation/withdrawal of participants from study

Each participant has the right to withdraw from the study at any time. Data can also be withdrawn at the participant's request at any time up until the point it is analysed.

Definition of End of Study

The BREATHE study is a planned 10 year cohort study. It is currently funded for 5 years. As a cohort study it will have continuous outcomes and as such we fully expect to secure funding for a further 5 years. At the end of 2 years we will have reported on the BREATHE-ILO sub-study outcomes.

[figure not shown]
As per our current funding the last patient will be recruited at 3 years after the study start date. After which, data will be collected on remaining patients up to 24 months (5 years). The end of study is the date that we have the final data lock.

DATA COLLECTION

The data sets outlined below include diagnostic and monitoring tests for all airways diseases and asthma-mimics. Each participant will have different information collected based on their diagnostic and treatment pathway.

First Appointment – Attendance at Complex Airways Clinic

At consent, participants will give permission for members of the approved research and clinical team to access their medical records. Researchers may use results found in the medical records or collected

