Re-discussion at CAMDT is proposed as a guide and it remains at the discretion of the lead clinician. Following diagnostics or specialist clinic referral, some patients may be re-discussed earlier in the interests of patient care. Follow-up in clinic is at the discretion of the clinician. Participants may be assigned to more than one treatment pathway as detailed below:

A. Biologics Pathway

- o Initiated on treatment within 4 weeks of discussion at CAMDT
- Biologics follow-up: 6 and 12 month follow-up as per departmental protocol with either an Airways clinician or RNS
- Lung function, FeNO, mini-AQLQ, ACQ7, clinical history and FBC.

B. Optimisation Pathway: Medications

- o Optimisation of inhaled therapy prior to commencing biologics
- Treatment for those not eligible for biologics including Th2 low disease, bronchiectasis, COPD

C. Optimisation Pathway: AHP

- o Referral to a specialist clinic and follow-up at the discretion of the specialist
- ILO; Newcastle Laryngeal Hypersensitivity Questionnaire, Vocal Cord Dysfunction Questionnaire
- o BPD; Nijmegen questionnaire, Breathing Pattern Assessment Tool

D. LVR Pathway

- This will require discussion at a specific LVR MDT with input from thoracic surgeons and satellite hospitals
- E. Diagnostics Pathway: It is at the discretion of the treating clinician when diagnostic tests will be reviewed and acted on. At a minimum, diagnostics will be re-discussed (if required) at a 6 month 'Follow-up CAMDT'
 - Physiology diagnostics will include: bronchodilator reversibility, provocation testing,
 FeNO, Lung volumes and gas transfer, 6MWT and oscillometry
 - o Imaging will include CXR, CT, DEXA, StratX assessment
 - o Cardiac Assessment will include ECG and echo
 - Blood testing will include Full blood count, Total IgE, Specific IgEs including Cat, Dog, House dust mite, Timothy Grass, Mixed moulds, Aspergillus, IgG Aspergillus, ANCA and Drug monitoring

Home Spirometry + MyAsthma/MyCOPD

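### BREATHE-ILO outcomes 4 and 5 are due in a report finished by 2 years, on largely immature follow-up, and the ILO/BPD follow-up list names no quality-of-life scale for outcome 5

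*Protocol*

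**What the plan says.** **Reporting date.** In the protocol's BREATHE-ILO sub-study section, five outcomes stand under the heading "Outcomes (Report of outcomes at 2 years". Outcome 4 is "An analysis of the predictors of response to interventions for ILO and BPD". Outcome 5 is "An analysis of whether the diagnosis and treatment of ILO and BPD improve quality of life for the patient and reduce treatment burden". Definition of End of Study repeats the date as a completed report: "At the end of 2 years we will have reported on the BREATHE-ILO sub-study outcomes".

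**Recruitment and follow-up.** The same section says that "the last patient will be recruited at 3 years after the study start date", with data then collected for up to 24 months, 5 years in all. Subsequent Visits sets reviews "at 6 (+/- 4months), 12(+/- 4months) and 24(+/- 4months) months after recruitment" and explains that these are not patient visits: "They are the timepoints at which the participants medical records are scrutinised". Sub-study recruitment uses the same processes as the platform. The text gives no sub-study recruitment stop, data cut or minimum follow-up.

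**Questionnaires.** Under Follow-up Streams, pathway C lists "ILO; Newcastle Laryngeal Hypersensitivity Questionnaire, Vocal Cord Dysfunction Questionnaire" and, for BPD, the Nijmegen questionnaire and the Breathing Pattern Assessment Tool. Mini-AQLQ is listed at the first appointment and at pathway A (biologics) follow-up. WEMWBS is listed at the first appointment only. Study Design rules out any questionnaire that is not part of routine care.

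**The concern.** Outcomes 4 and 5 can be answered only with data recorded after an ILO or BPD intervention. A report finished at 2 years of study time falls a year before platform recruitment ends, and many participants will then lack the later reviews. Follow-up in clinic, and the timing of re-discussion, are at the clinician's discretion. If the 2-year analysis simply uses whoever has a follow-up record, inclusion depends on who was seen early. That may be related to severity or to how treatment is going, and it would bias both the response rate and its predictors.

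The second problem is one of answerability. Showing that quality of life improved needs the same scale before and after treatment. The follow-up list for the stream that treats ILO and BPD does not supply one, and the design does not allow one to be added.

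**Working it through.** **The plan's own timeline.** Recruitment to month 36 plus 24 months of follow-up gives 36 + 24 = 60 months = 5 years, as stated.

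**Inputs.** Reviews at 6, 12 and 24 months, each ±4 months (Subsequent Visits). Report complete by month 24 (Definition of End of Study). Two assumptions are not in the protocol: uniform accrual from month 0, continuing to the data cut, and a data cut at month 24, the latest possible.

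**Formula.** With data cut C and uniform accrual stopping at month S, the share of recruits with at least t months since recruitment is min(S, C − t)/S. With C = S = 24 this is (24 − t)/24.

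| Review | Window opens / nominal / closes (months) | In-window review possible | Nominal time reached | Window closed |
|---|---|---|---|---|
| 6 months | 2 / 6 / 10 | 22/24 = 91.7% | 18/24 = 75% | 14/24 = 58.3% |
| 12 months | 8 / 12 / 16 | 16/24 = 66.7% | 12/24 = 50% | 8/24 = 33.3% |
| 24 months | 20 / 24 / 28 | 4/24 = 16.7% | 0/24 = 0% | 0% |

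**Sensitivity to the assumptions.**

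- *Earlier cut.* With C = S = 18, the nominal shares are 12/18 = 66.7% at 6 months and 6/18 = 33.3% at 12 months. No in-window 24-month review is possible, because month 20 has not been reached.
- *Earlier accrual stop.* With C = 24, the nominal 12-month share is 12/18 = 66.7% if accrual stops at month 18 and 12/12 = 100% if it stops at month 12. The in-window 24-month share is then 4/18 = 22.2% or 4/12 = 33.3%.
- *Both.* With C = 21 and S = 18, the nominal 12-month share is 9/18 = 50% and the in-window 24-month share is 1/18 = 5.6%.
- *Accrual shape*, with C = S = 24 and u = (24 − t)/24. For linearly rising accrual the share is u²; for linearly falling accrual it is 1 − (1 − u)². At t = 12, u = 1/2, giving 25% and 75%. At t = 20, u = 1/6, giving 2.8% and 30.6%.

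**Which horizon matters.** The protocol attaches no follow-up time to outcomes 4 and 5. As extracted, the CAMDT table marks ILO assessment for re-discussion at 6 months and the disordered breathing clinic at 12 months, although its layout is partly broken. On that reading the 6-month column bears on ILO and the 12-month column on BPD; both conditions are named in outcomes 4 and 5.

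**Quality-of-life scales by time.**

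| Scale | First appointment | Pathway A follow-up | Pathway C follow-up |
|---|---|---|---|
| Mini-AQLQ | listed | listed | not listed |
| WEMWBS | listed | not listed | not listed |

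The four tools that pathway C lists are not named in the protocol as quality-of-life scales.

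**The case against.** Four stronger readings are tempting, and the protocol does not support them.

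- *Nobody could have a 24-month review by year 2.* The window opens at month 20, so anyone recruited in months 0 to 4 could have one. The share is zero only for a full 24 months, or for a cut at month 20 or earlier.
- *At most half have reached 12 months.* Fifty per cent is the result of one accrual assumption, not a bound. Two-thirds could have an in-window 12-month review under the same assumption.
- *All five outcomes are premature.* Outcomes 1 to 3 (incidence, and predictors of having ILO or BPD) do not need follow-up after treatment.
- *There would be no quality-of-life follow-up at all.* Participants may be on several pathways, and those also on pathway A would have mini-AQLQ at follow-up. Pathway C follow-up is at the specialist's discretion, the list is not said to be exhaustive, and the whole record is reviewed. Treatment burden may be recoverable from medication records.

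It can also be said that identical recruitment processes do not imply identical duration, and that the missing timeline figure or flow chart may show a sub-study stop. That is fair, and the conclusion is conditional on it. A data cut and denominator rule are often left to the SAP. Here, however, the reporting date, the outcomes and the questionnaires are all fixed in the protocol, and they do not fit together.

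Finally, restricting the analysis by recruitment date also selects early recruits. That is true, but a calendar rule does not depend on how a patient is doing, whereas being seen early may.

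**Conclusion.** The point holds for outcomes 4 and 5. Under uniform accrual and a month-24 cut, about 17% of recruits could have an in-window 24-month review. Half have reached a nominal 12 months (67% could have an in-window review; the window has closed for 33%). Three-quarters have reached a nominal 6 months (window closed for 58%). Time for cleaning and reporting means an earlier cut, which generally lowers these shares; an earlier sub-study recruitment stop would raise them. An early look at response is therefore feasible at 2 years, but a mature answer is not.

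The gap in outcome 5 is independent of these assumptions. The listed ILO/BPD follow-up stream names no quality-of-life scale, so a before-and-after comparison is assured by the listed schedule only for participants who are also on pathway A. Such a subgroup is selected by its treatment and need not represent ILO or BPD patients in general.

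**What to change.** 1. Keep outcomes 1 to 3 in the 2-year report, with a stated data cut.
2. For outcomes 4 and 5, report at that time only early (6-month) response, labelled interim. Include all participants recruited at least 10 months before the cut, so that the 6-month window has closed for everyone in the denominator. With a month-24 cut this means recruitment by month 14, or 14/24 = 58.3% under uniform accrual. State how many of them have no follow-up record.
3. Report 12- and 24-month results for outcomes 4 and 5, including BPD, at the final lock.
4. Reword outcome 5 to the questionnaires that pathway C records. Report quality of life only for participants with a routine mini-AQLQ (or WEMWBS) before and after, and state their number and how they came to have both. The two laryngeal questionnaires are not on the first-appointment list, so change on them can be reported only where the pathway C record holds both values.
5. If the sub-study has its own recruitment stop, state it in the text.

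This is a change of protocol wording with no new data collection. The cost is that the long-term ILO/BPD result comes later and the quality-of-life claim is narrower.
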